16.23 Accrual Time and Study Duration

The anticipated accrual rate is approximately 2 patients per month. Therefore, the accrual period for this phase II study is expected to be between 7.5 and 14 months, depending upon whether patients are accrued beyond the first stage. The final analysis can begin approximately 18 months after the trial begins, i.e. as soon as the last patient has been observed for 4 months.

16.24 Power and Significance Level

Assuming that the number of successes is binomially distributed, the significance level is 0.05 and the probability of declaring that this regimen warrants further studies (i.e. statistical power) under various success proportions and the

probability of stopping accrual after the first stage can be tabulated as a function of the true success proportion as shown in the following table.

If the true success proportion is . . .	0.1	0.15	0.2	0.25	0.30
then the probability of declaring that the regimen warrants further studies is . . .	0.033	0.160	0.383	0.622	0.807

16.25 Other Considerations

Adverse events, quality/duration of response, and patterns of treatment failure observed in this study, as well as scientific discoveries or changes in standard care will be taken into account in any decision to terminate the study.

16.3 Analysis Plan

The analysis for this trial will commence at planned time points (see 16.2) and at the time the patients have become evaluable for the primary endpoint. Such a decision will be made by the Statistician and Study Chair, in accord with CCS Standard Operating Procedures, availability of data for secondary endpoints (eg, laboratory correlates), and the level of data maturity. It is anticipated that the earliest date in which the results will be made available via manuscript, abstract, or presentation format is when patients have been on study for 16 weeks (i.e. received second scan).

16.31 Primary Endpoint

16.311 **Definition:** The primary endpoint of this trial is the progression-free survival rate. This is defined as the proportion of evaluable patients who are progression-free (stable disease, partial response, complete response) at 16 weeks. All patients meeting the eligibility criteria who have signed a consent form and have begun treatment will be considered evaluable.

16.312 **Estimation:** The proportion of successes will be estimated by the number of successes divided by the total number of evaluable patients. Confidence intervals for the true success proportion will be calculated according to the approach of Clopper and Pearson.

16.316 **Over Accrual:** If more than the target number of patients are accrued, the additional patients will not be used to evaluate the stopping rule or used in any decision making processes; however, they will be included in final point estimates and confidence intervals as though they were accrued in the final stage.

16.32 Secondary Endpoints

The following endpoints will be evaluated: overall response rate, progression-free survival, overall survival, and adverse events.

16.321 **Overall Response Rate (ORR):** Overall response rate is defined as the proportion of patients who experience either a partial response or complete response by the given time point. ORR will be reported descriptively and a 95% confidence interval will be reported.

16.322 **Progression-Free Survival:** Progression-free survival is defined as the time from study entry to the first of either disease progression or death from any cause, where disease progression will be determined based on

RECIST 1.1 criteria. PFS will be estimated using the Kaplan-Meier method. The median PFS and 95% confidence interval will be reported. Patients will be censored at the last disease assessment date.

16.323 Overall Survival (OS): Overall survival is defined as the time from study entry to death from any cause. OS will be estimated using the Kaplan-Meier method. The median OS and 95% confidence interval will be reported. Patients will be censored at the date patient was last known to be alive.

16.324 Adverse events: The maximum grade for each type of adverse event by patient will be summarized by frequencies and percentages using CTCAE version 4.0. We will also closely monitor adverse events throughout the study.

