11.1 Schedule of Evaluations

For the purposes of this study, patients should be reevaluated every 8 weeks. In addition to a baseline scan, confirmatory scans should also be obtained 8 weeks following initial documentation of objective response.

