- FDG-PET: FDG-PET scanning is allowed to complement CT scanning in assessment of progressive disease [PD] and particularly possible 'new' disease. A 'positive' FDG-PET scanned lesion is defined as one which is FDG avid with an update greater than twice that of the surrounding tissue on the attenuation corrected image; otherwise, an FDG-PET scanned lesion is considered 'negative.' New lesions on the basis of FDG-PET imaging can be identified according to the following algorithm:
 - a. Negative FDG-PET at baseline with a positive FDG-PET at follow-up is a sign of PD based on a new lesion.
 - b. No FDG-PET at baseline and a positive FDG-PET at follow-up:

- i. If the positive FDG-PET at follow-up corresponds to a new site of disease confirmed by CT, this is PD.
- ii. If the positive FDG-PET at follow-up is not confirmed as a new site of disease on CT at the same evaluation, additional follow-up CT scans (i.e., additional follow-up scans at least 4 weeks later) are needed to determine if there is truly progression occurring at that site. In this situation, the date of PD will be the date of the initial abnormal PDG-PET scan.
- iii. If the positive FDG-PET at follow-up corresponds to a pre-existing site of disease on CT that is not progressing on the basis of the anatomic images, it is not classified as PD.

11.33 Measurement at Follow-up Evaluation:

A subsequent scan must be obtained 8 weeks following initial documentation of an objective status of either complete response (CR) or partial response (PR).

In the case of stable disease (SD), follow-up measurements must have met the SD criteria at least once after study entry at a minimum interval of 8 weeks (see Section 11.44).

The cytological confirmation of the neoplastic origin of any effusion that appears or worsens during treatment when the measurable tumor has met criteria for response or stable disease is mandatory to differentiate between response or stable disease (an effusion may be a side effect of the treatment) and progressive disease.

- Cytologic and histologic techniques can be used to differentiate between PR and CR in rare cases (e.g., residual lesions in tumor types such as germ cell tumors, where known residual benign tumors can remain.)

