11.43 Response Criteria

11.431 All target lesions and target lymph nodes followed by CT/MRI/PET-CT/Chest X-ray/physical examination must be measured on re-evaluation at evaluation times specified in Section 11.1. Specifically, a change in objective status to either a PR or CR cannot be done without re-measuring target lesions and target lymph nodes.

Note: Non-target lesions and non-target lymph nodes should be evaluated at each assessment, especially in the case of first response or confirmation of response. In selected circumstances, certain non-target organs may be evaluated less frequently. For example, bone scans may need to be repeated only when complete response is identified in target disease or when progression in bone is suspected.

11.432 Evaluation of Target Lesions

Complete Response (CR): All of the following must be true:

- Disappearance of all target lesions.
- Each target lymph node must have reduction in short axis to <1.0 cm.

Partial Response (PR): At least a 30% decrease in PBSD (sum of the longest diameter for all target lesions plus the sum of the short axis of all the target lymph nodes at current evaluation) taking as reference the BSD (see Section 11.41).

Progression (PD): At least one of the following must be true:

- At least one new malignant lesion, which also includes any lymph node that was normal at baseline (<1.0 cm short axis) and increased to ≥ 1.0 cm short axis during follow-up.
- At least a 20% increase in PBSD (sum of the longest diameter for all target lesions plus the sum of the short axis of all the target lymph nodes at current evaluation) taking as reference the

MSD (Section 11.41). In addition, the PBSD must also demonstrate an absolute increase of at least 0.5 cm from the MSD.

- c. See Section 11.32 for details in regards to the requirements for PD via FDG-PET imaging.

Stable Disease (SD): Neither sufficient shrinkage to qualify for PR, nor sufficient increase to qualify for PD taking as reference the MSD.

11.433 Evaluation of Non-Target Lesions & Non-target Lymph Nodes

Complete Response (CR): All of the following must be true:

- a. Disappearance of all non-target lesions.
- b. Each non-target lymph node must have a reduction in short axis to <1.0 cm.

Non-CR/Non-PD: Persistence of one or more non-target lesions or non-target lymph nodes.

Progression (PD): At least one of the following must be true:

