11.44 Overall Objective Status

The overall objective status for an evaluation is determined by combining the patient's status on target lesions, target lymph nodes, non-target lesions, non-target lymph nodes, and new disease as defined in the following tables:

11.441 For Patients with Measurable Disease

Target Lesions & Target Lymph Nodes	Non-Target Lesions & Non-Target Lymph Nodes	New Sites of Disease	Overall Objective Status
CR	CR	No	CR
CR	Non-CR/Non-PD	No	PR
PR	CR Non-CR/Non-PD	No	PR
CR/PR	Not All Evaluated*	No	PR**

Target Lesions & Target Lymph Nodes	Non-Target Lesions & Non-Target Lymph Nodes	New Sites of Disease	Overall Objective Status
SD	CR Non-CR/Non-PD Not All Evaluated*	No	SD
Not all Evaluated	CR Non-CR/Non-PD Not All Evaluated*	No	Not Evaluated (NE)
PD	Unequivocal PD CR Non-CR/Non-PD Not All Evaluated*	Yes or No	PD
CR/PR/SD/PD/Not all Evaluated	Unequivocal PD	Yes or No	PD
CR/PR/SD/PD/Not all Evaluated	CR Non-CR/Non-PD Not All Evaluated*	Yes	PD

*See Section 11.431

** NOTE: This study uses the protocol RECIST v1.1 template dated 2/16/2011. For data collection and analysis purposes the objective status changed from SD to PR in the MCCC protocol RECIST v1.1 template as of 2/16/2011 and to match RECIST v1.1 requirements.

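### ORR in Section 16.321 counts any CR or PR and makes no use of the confirmatory scan in Sections 11.1 and 11.33, so a response not sustained at that scan still counts

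*Combined protocol and SAP*

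**What the plan says.** Section 16.321 counts patients who "experience either a partial response or complete response by the given time point" and adds that "ORR will be reported descriptively and a 95% confidence interval will be reported". It sets no confirmation condition, does not say which time point is meant, and gives the denominator only as patients. It names no interval method.

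Section 11 treats the scan after a first response as something distinct:

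- Section 11.1: "patients should be reevaluated every 8 weeks", and "confirmatory scans should also be obtained 8 weeks following initial documentation of objective response".
- Section 11.33: "A subsequent scan must be obtained 8 weeks following initial documentation of an objective status" of CR or PR.
- Section 11.431 asks for non-target disease to be evaluated at each assessment, "especially in the case of first response or confirmation of response", so it separates the first response from its confirmation.
- Section 11.44 works one evaluation at a time: "The overall objective status for an evaluation is determined by combining" the target, non-target and new-disease findings. Neither it nor any other section defines a best overall or a confirmed response.

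Section 16.311 does define evaluable patients (eligible, consented, treatment begun), and Section 16.312 names Clopper and Pearson. Both are written for the primary endpoint.

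**The concern.** The protocol asks for a repeat scan after each first response and, in Section 11.1, calls that scan confirmatory. The analysis section then defines the response rate so that the result of that scan cannot change it. A patient read as PR once, and no longer PR at the required scan, is a responder under 16.321.

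The trial has one arm and few patients, so a single reading near the 30% shrinkage threshold moves the rate visibly. Section 11.44 also allows an overall PR when not all non-target disease was evaluated. Response is used elsewhere too: as an outcome for the correlative work (Sections 2.31 and 16.331), and, in its quality and duration, as one consideration in any decision to terminate the study (Section 16.25). Two analysts following the text could report different ORRs from the same data.

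**Working it through.** **1. The plan's own figures.** The plan gives no expected ORR, no ORR precision and no ORR sample size. Its only operating figures concern the primary endpoint: at least 6 successes in 25. The exact tail P(X ≥ 6 | n = 25, p) gives 0.0334 at p = 0.10 (Section 16.24 states 0.033) and 0.8065 at p = 0.30 (0.807). At 0.15, 0.20 and 0.25 it gives 0.1615, 0.3833 and 0.6217 (0.160, 0.383 and 0.622; the first differs slightly in the third decimal). ORR enters none of these.

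**2. Direction.** Over the same patients and the same follow-up, every confirmed responder is also an any-CR/PR responder. Hence any-response rate ≥ confirmed rate, with equality when no response fails confirmation.

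**3. Size of one unconfirmed response.** It is 1/n: 1/25 = 4.0 points for the 25 evaluable patients, and 1/28 = 3.6 points at maximum accrual (Section 16.22).

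**4. Intervals.** Clopper-Pearson 95% is assumed for ORR, as 16.321 names no method. The lower limit is the 0.025 quantile of Beta(x, n − x + 1), and 0 if x = 0. The upper limit is the 0.975 quantile of Beta(x + 1, n − x).

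| Responders | n = 25 | n = 28 |
|---|---|---|
| 0 | 0% (0 to 13.7) | 0% (0 to 12.3) |
| 1 | 4.0% (0.1 to 20.4) | 3.6% (0.1 to 18.3) |
| 2 | 8.0% (1.0 to 26.0) | 7.1% (0.9 to 23.5) |
| 3 | 12.0% (2.5 to 31.2) | 10.7% (2.3 to 28.2) |

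So if two of 25 patients respond and one is not confirmed, the any-response rate is 8.0% and the confirmed rate 4.0%, with heavily overlapping intervals.

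**5. Range under assumed failure of confirmation.** With any-response rate r and share q of first responses not confirmed, the difference is r × q. The documents give no q, so it is assumed. The values of r are the response rates quoted in the background: 1.6% for this drug in colorectal cancer (Section 1.2), and 10% and 32% as the ends of the range for first-line single-agent 5-fluorouracil (Section 1.3). None of them is a forecast for this trial.

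| r | q = 0 | q = 10% | q = 25% | q = 50% |
|---|---|---|---|---|
| 1.6% | 0 | 0.2 points | 0.4 | 0.8 |
| 10% | 0 | 1.0 | 2.5 | 5.0 |
| 32% | 0 | 3.2 | 8.0 | 16.0 |

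**6. Timing.** With 8-weekly scans, a response first seen at week 16 can be confirmed only at about week 16 + 8 = 24. If the unnamed time point were 16 weeks, only responses first seen at about week 8 could be confirmed by then. Section 4.1 (footnote 6) allows imaging up to 7 days before Day 1 of odd-numbered cycles. Two on-schedule scans, without cycle delays, can therefore lie 56 − 7 = 49 to 56 + 7 = 63 days apart. A rule demanding at least 56 days would reject some patients scanned on schedule.

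**The case against.** The best reply is that nothing is broken. ORR is secondary and descriptive, and it plays no part in the decision rule, the power or the sample size. An unconfirmed response rate can be reported legitimately. Section 18.5 requires supporting documentation of response, and Section 16.25 already looks at the quality and duration of responses. All of this stands, and it limits the point to a cheap improvement.

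A reader might infer more from the text than it carries:

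- *That the plan intended a confirmed ORR and 16.321 contradicts it.* Section 11.1 says the scans should be obtained and Section 11.33 that one must be, but neither says that an unconfirmed CR or PR is downgraded. This is a gap between sections, not proof of intent.
- *That the reported rate will be inflated.* This needs at least one response to fail confirmation, and the documents give no such rate.
- *That the undefined time point also pushes the rate up.* It can act either way: an early cut-off misses later responses, and open-ended follow-up picks them up.
- *That local, unblinded reading makes the error worse.* No section says who reads the scans for the endpoint. Central review is simply not mentioned.
- *That one or two readings could be the whole result because the drug's response rate is 1.6%.* That figure is from colorectal cancer. The biliary figures quoted for another fluoropyrimidine are 10-32%, in the first line.

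One practical objection also stands. Patients who stop treatment for reasons other than progression go to event monitoring (Section 13.3), and the schedule in Section 4.2 lists no imaging. Their end-of-treatment scan need not fall at the confirmation point. A confirmed ORR would count such responders as unconfirmed, so they must be shown.

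**Conclusion.** The point holds as a minor one. Section 16.321 makes no use of the confirmatory scan, and no other section corrects this, so a response not sustained at that scan still counts. The rate can equal or exceed the confirmed rate by 4.0 points per unconfirmed response at n = 25, or 3.6 at n = 28. The total difference is unknown and may be zero; the range in the table rests on assumed failure shares. The primary test, its alpha of 0.033 and its power of 0.807 do not change.

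The missing time point, denominator and interval method are lesser gaps that would not justify a comment alone, but the same sentence can close them. Confirmed ORR is preferable because it is less exposed to a single measurement error and draws on a scan the protocol already requires.

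**What to change.** In Section 16.321:

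- Define confirmed ORR as a CR or PR maintained at the next scheduled evaluation after it is first documented, nominally 8 weeks later and within the Section 4.1 scan windows rather than at a rigid 56 days.
- Take it as best response over all assessments before progression or other anticancer therapy. This replaces the unnamed time point.
- Use the patients evaluable under 16.311 as the denominator, with a Clopper-Pearson 95% interval as in 16.312.
- Report the any-CR/PR rate beside it.
- List separately the responders who left treatment without a confirmatory scan, and mark any whose scan is still due at the data cut-off.

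The cost is a few sentences and one extra line in the results table; no scan is added. The downside is that the confirmed rate may be lower than the any-response rate, and responders with no confirmatory scan do not count as confirmed. Showing both rates and the list lets the reader see how much of any difference is loss of response and how much is a missing scan.

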1.4 Study Design

This is the single arm phase II trial to assess the efficacy of FTD/TPI in advanced, refractory BTCs. The primary end point of this study is 16-week progression-free survival. If 30% of patients remain progression-free at 16-weeks, this trial will be considered a success warranting bigger trials. We will accrue 25 evaluable patients using a single stage design. The total sample size of this study is 28 to account for 3 possible non-evaluable subjects.

Patient will receive FTD/TPI at the dose of 35 mg/m² on Days 1-5 and 8-12 of 28-day cycle. Patient will receive treatment until disease progression or unacceptable toxicities. Patients will undergo restaging scans every 2 cycles. Subjects will be monitored for adverse events from the beginning of the study drug to 28 days after the last dose. We will collect blood samples for determination of cell free DNA and circulating tumor cells at baseline, after 2 cycles and at progression.

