6.8 Baseline symptoms

All required baseline symptoms (see [Section 10.6](#)) must be documented and graded.

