10.0 Adverse Event (AE) Monitoring and Reporting

The site principal investigator is responsible for reporting any/all serious adverse events to the sponsor as described within the protocol, regardless of attribution to study agent or treatment procedure.

The sponsor/sponsor-investigator is responsible for notifying FDA and all participating investigators in a written safety report of any of the following:

- Any suspected adverse reaction that is both serious and unexpected.
- Any findings from laboratory animal or *in vitro* testing that suggest a significant risk for human subjects, including reports of mutagenicity, teratogenicity, or carcinogenicity.
- Any findings from epidemiological studies, pooled analysis of multiple studies, or clinical studies, whether or not conducted under an IND and whether or not conducted by the sponsor, that suggest a significant risk in humans exposed to the drug
- Any clinically important increase in the rate of a serious suspected adverse reaction over the rate stated in the protocol or Investigator's Brochure (IB).

Summary of SAE Reporting for this study
(please read entire section for specific instructions):

WHO:	WHAT form:	WHERE to send:
All sites	Pregnancy Reporting http://ctep.cancer.gov/protocolDevelopment/electronic_applications/docs/PregnancyReportFormUpdated.pdf	Mayo Sites – attach to MCCC Electronic SAE Reporting Form and submit to [REDACTED]
Mayo Clinic Sites	Mayo Clinic Cancer Center SAE Reporting Form http://livelcycle2.mayo.edu/workspace/?startEndpoint=MC4158-56/Processes/MC4158-56-Process.MC4158-56 AND attach MedWatch 3500A: http://www.fda.gov/downloads/AboutFDA/ReportsManualsForms/Forms/UCM048334.pdf	Submit to [REDACTED] Will automatically be sent to [REDACTED]

Definitions

Adverse Event

Any untoward medical occurrence associated with the use of a drug in humans, whether or not considered drug related.

Suspected Adverse Reaction

Any adverse event for which there is a reasonable possibility that the drug caused the adverse event.

Expedited Reporting

Events reported to sponsor within 24 hours, 5 days or 10 days of study team becoming aware of the event.

Routine Reporting

Events reported to sponsor via case report forms

Events of Interest

Events that would not typically be considered to meet the criteria for expedited reporting, but that for a specific protocol are being reported via expedited means in order to facilitate the review of safety data (may be requested by the FDA or the sponsor).

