10.6 Required Routine Reporting

10.61 Baseline and Adverse Events Evaluations

Pretreatment symptoms/conditions to be graded at baseline and adverse events to be graded at each evaluation.

Grading is per CTCAE v4.0 **unless** alternate grading is indicated in the table below:

CTCAE System/Organ/Class (SOC)	Adverse event/Symptoms	Baseline	Each evaluation
Blood and lymphatic system disorders	Anemia	X	X
Gastrointestinal Disorders	Abdominal Pain	X	X
	Baseline # of stools	X	
	Diarrhea		X
	Nausea	X	X
	Vomiting	X	X
General disorders	Fatigue	X	X
Investigations	Neutrophil count decreased	X	X
	Platelet count decreased	X	X
Metabolism and nutrition disorders	Anorexia	X	X

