10.62 All other AEs

Submit via appropriate MCCC Case Report Forms (i.e., paper or electronic, as applicable) the following AEs experienced by a patient and not specified in Section 10.6:

10.621 Grade 2 AEs deemed *possibly, probably, or definitely* related to the study treatment or procedure.

10.622 Grade 3 and 4 AEs regardless of attribution to the study treatment or procedure.

10.623 Grade 5 AEs (Deaths)

10.6231 Any death within 30 days of the patient's last study treatment or procedure regardless of attribution to the study treatment or procedure.

10.6232 Any death more than 30 days after the patient's last study treatment or procedure that is felt to be at least possibly treatment related must also be submitted as a Grade 5 AE, with a CTCAE type and attribution assigned.

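### Section 16.324 tabulates maximum adverse-event grade without using the required baseline grades, so a pre-existing symptom that persists unchanged counts as an on-study event

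*Combined protocol and SAP*

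**What the plan says.** The analysis rule for safety is one sentence in Section 16.324: "The maximum grade for each type of adverse event by patient will be summarized by frequencies and percentages using CTCAE version 4.0". It names no treatment-emergent definition, baseline rule, attribution rule, time window or analysis set.

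The data that feed the table are set out in two places.

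- **Listed terms (10.61).** The instruction is "Pretreatment symptoms/conditions to be graded at baseline and adverse events to be graded at each evaluation". Eight terms are marked in both columns: anemia, abdominal pain, nausea, vomiting, fatigue, neutrophil count, platelet count and anorexia. Diarrhea is marked at each evaluation only; its baseline entry is "Baseline # of stools". Section 6.8 makes the baseline part compulsory: required baseline symptoms "must be documented and graded".
- **All other terms (10.62).** This section covers "the following AEs experienced by a patient and not specified in Section 10.6". Grade 2 enters only as "Grade 2 AEs deemed *possibly, probably, or definitely* related to the study treatment or procedure". Grades 3 and 4 enter whatever the attribution. Deaths enter if they fall within 30 days of the last treatment, or later if at least possibly related. Grade 1 is not mentioned. Sections 10.1 and 10.41 add one exception: events reported expeditiously also go into the routine data, and these include grade 1 and 2 events with hospitalization of 24 hours or more.

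**The concern.** The trial enrolls patients with advanced biliary tract cancer after at least one prior line of therapy, with performance status 0 or 1 and no hemoglobin limit at entry (3.1). Some will start treatment already anemic, tired or in pain. The plan grades those symptoms before treatment and again at each visit, then reports only the highest grade. Nothing in the table separates a symptom the patient brought into the trial from one that appeared or worsened on the drug.

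Safety and tolerability are a named secondary goal (2.21), and the trial has a single arm. No concurrent control group would carry the same background and so reveal it.

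A second, smaller matter is that listed and unlisted terms are collected to different depths but fall under the same summary sentence. A reader of the table would not know that the low grades are incomplete for one set.

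**Working it through.** The plan states no figure for this table, so there is none to reproduce. The check is a reading of the sections together, followed by an illustration of size.

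**Step 1. What happens to a persisting symptom.** Take a patient with grade 1 fatigue at baseline and grade 1 at every visit. Under 10.61 the fatigue is graded at baseline and at each evaluation. Under 16.324 the maximum is grade 1, and the patient is counted as having fatigue. The baseline grade is on file, but no step in 16.324 compares it with the maximum.

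**Step 2. Size for a listed term.** Let *b* be the proportion with the symptom at baseline, *s* the share of those who show it again on treatment at no higher grade, and *t* the rate of new onset among patients free of it at baseline. Patients who worsen count in both versions of the table, so they cancel. The excess of the planned any-grade rate over the treatment-emergent rate is *b* × *s*, at most *b* (when *s* = 1).

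The documents give neither *b* nor *s*, so these are assumptions. With *s* = 1, the planned rate is *b* + (1 − *b*)*t* and the treatment-emergent rate is (1 − *b*)*t*. Taking *t* = 50% for illustration and n = 28 (maximum accrual, 16.22):

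| Assumed *b* | Planned rate | Treatment-emergent rate | Excess patients (28 × *b*) |
|---|---|---|---|
| 10% | 0.10 + 0.90 × 0.50 = 55% | 45% | 2.8 |
| 20% | 0.20 + 0.80 × 0.50 = 60% | 40% | 5.6 |
| 35% | 0.35 + 0.65 × 0.50 = 67.5% | 32.5% | 9.8 |

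The excess does not depend on *t*. With the 25 evaluable patients as denominator it runs from 25 × 0.10 = 2.5 to 25 × 0.35 = 8.75. If only half of the baseline symptoms persist without worsening (*s* = 0.5), it halves: at *b* = 35%, 28 × 0.35 × 0.5 = 4.9.

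**Step 3. Terms where the effect is smaller or different.** Entry requires an ANC of at least 1500/mm³ and platelets of at least 100,000/mm³ (3.15), which limits baseline abnormality for those two terms. Diarrhea has no baseline grade, so a grade-against-grade comparison is not possible; the recorded stool count is its only reference.

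**Step 4. Unlisted terms.** Under 10.62, with the exception for serious events, what is missing is non-serious grade 1 and non-serious grade 2 judged unrelated or unlikely. Table 1 in Section 1.2 shows the kind of term involved. On the drug, pyrexia was 19% all grades and 1% grade 3-4, stomatitis 8% and <1%, dysgeusia 7% and 0%, alopecia 7% and 0%. None of these is on the 10.61 list. Taking <1% as 0.5%, the four sum to 41% and 1.5%, so (41 − 1.5)/41 = 96% of those occurrences were grade 1 or 2. Table 1 does not split grade 1 from grade 2, so the share that 10.62 would miss cannot be computed; it could be anywhere from near none to all of the low-grade events.

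**The case against.** The strongest reply is that the alleged error is read into a silence. Section 10.61 itself separates pretreatment conditions from adverse events. Section 10.0 defines an adverse event as "Any untoward medical occurrence associated with the use of a drug in humans, whether or not considered drug related", and Section 1.4 says "Subjects will be monitored for adverse events from the beginning of the study drug to 28 days after the last dose". On that reading, a symptom seen only before treatment is not an adverse event and would not be tabulated.

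Part of this stands. A reader might infer that the baseline records themselves are counted as events; the documents do not say so, although the test schedule in 4.1 does mark an adverse event assessment at screening. But the reply does not reach a symptom that continues. It is graded again after the drug has started, inside the monitoring window, and the definition applies whether or not the drug caused it. Only a comparison with baseline would take it out, and none is planned.

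Other stronger readings are tempting and are not supported:

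- **Placebo rates as the size of the error.** A reader might use the placebo column of Table 1 (fatigue 35%, anemia 33%). Those are adverse-event rates from a colorectal cancer trial, not the prevalence of symptoms before treatment. A symptom that newly arose on placebo would also still exceed baseline under the proposed rule.
- **Loss of most low-grade events.** Related grade 2 events and serious events are kept, and no grade 1 versus grade 2 split is given, so "most" cannot be shown. Nor does leaving out unrelated grade 2 events understate drug toxicity if attribution is right.
- **Rates not comparable with Table 1.** No such comparison is planned, and the documents do not say how that table treated baseline symptoms.
- **Effect on severe events or stopping.** The limit in 10.62 leaves grade 3-4 collection complete. The stopping rule in 16.42 uses grade 4 or higher events at least possibly related, so that limit does not touch it.

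It is also fair to say that targeted collection is a legitimate choice in a trial of 28 patients, and that 10.62 states its limits openly. For unlisted terms the matter is therefore mainly one of labelling.

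**Conclusion.** The concern holds for the eight terms graded both at baseline and on treatment. As written, the table counts persisting, unchanged symptoms as on-study events, although the grades needed to separate them are required. The any-grade frequency of a term can be overstated by up to the baseline prevalence of symptoms that persist without worsening. That is about 3 to 10 of 28 patients at an assumed prevalence of 10% to 35%, with less room for neutrophils and platelets. The direction follows from the plan; the size rests on assumed prevalence, on full persistence and on 28 as the denominator.

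For terms outside 10.61, any-grade frequencies are incomplete by design, by an amount the documents do not allow one to compute. This is a minor addition. The efficacy decision, which rests on 16-week progression-free survival, does not use this table.

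**What to change.** In 16.324:

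1. For the eight terms, tabulate the maximum on-study grade only when it exceeds the patient's baseline grade, and show baseline grade beside maximum grade.
2. For diarrhea, report the on-study grade and read it against the recorded baseline stool count.
3. For terms outside 10.61, report grade 3 or higher regardless of attribution and related grade 2. Give no all-grade total, and footnote that non-serious grade 1 and non-serious unrelated grade 2 events were not collected.
4. Name the analysis set and the on-study window. Section 1.4 ends monitoring 28 days after the last dose, while 4.1 and 10.41 use 30 days; these passages must be reconciled.

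The cost is a few sentences and table programming. No new data are needed, because 6.8 and 10.61 already require the baseline grades and the stool count.
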